7.5.2 Patient Reported Outcomes

We will collect PROs using REDCap, which is already in throughout the institution by several clinical investigations. PROs will include questionnaires regarding physical function, pain, fatigue, mental well-being, endocrine symptoms, sleep, sexual function, and medication adherence, at baseline, 2, and 6 months following initiation of the intervention. Pain, fatigue, mental well-being, sleep, and physical function will be assessed using the NIH PROMIS questionnaire; endocrine symptoms with the FACT-endocrine symptoms, and sexual function

with the MOS-Sexual Function. Medication adherence will be monitored with the institutional drug diary.

Enrolled patients will be given a letter with a username and password for the Fitbit website, and will be oriented on how to use the website; an email address will also be recorded for each participant. Participants will receive e-mail reminders when it is time for them to complete the REDCap questionnaire. They will be encouraged to complete the questionnaire prior to any planned clinic visit; however, they will be informed that a research coordinator can assist them prior to their visit if they prefer to complete the questionnaire at the clinic. Whether patients complete the PRO questionnaire at home or in the clinic, they will access the questionnaires via the internet. At follow-up clinic visits for patients who completed the PRO questionnaires, clinician sub-investigators will have a summary report available to them via REDCap.

Questionnaires will focus on some basic background information and patient reported outcomes, with more detailed survey information as follows. Data from the questionnaires will be available for export into spreadsheets or other tools for analysis.

NOTE: In the event that questionnaires through REDCap are not available, we will use paper-based questionnaires.

The questions that will be included in the REDCap system are included in Appendix E. Score interpretation is in Appendix F. Domains that will be included in REDCap are as follows:

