the impact of fatigue on physical, mental, and social activities. The short form used has 7 questions which assess fatigue over the past seven days. As with all of the PROMIS short forms, each question has five response options ranging in value from one to five. A total raw score is calculated by summing the values of the response to each question, and then translated into a T-score using a conversion table. The T-score rescales the raw score into a standardized score with a mean of 50 and a standard deviation (SD) of 10. Therefore, a person who has a T-score of 40 is one SD below the U.S. general population mean. Reliability and validity of the fatigue assessment in cancer patients has been reported 104.

- Mental health will be evaluated using the NIH PROMIS Depression and Anxiety questionnaires. The Adult Depression Version 1.0 Short Form is an 8 question survey, and the Adult Anxiety Version 1.0 Short Form is a 7-item survey, for a total of 15 mental health questions. The depression item bank assesses self-reported negative mood (sadness, guilt), views of self-criticism, worthlessness), and social cognition (loneliness, interpersonal alienation), as well as decreased positive affect and engagement (loss of interest, meaning, and purpose). The anxiety item bank measures self-reported fear (fearfulness, panic), anxious misery (worry, dread), hyperarousal (tension, nervousness, restlessness), and somatic symptoms related to arousal (racing heart, dizziness). The anxiety and depression scores are calculated individually, in the same way all PROMIS scores are calculated as above.
- Endocrine symptoms will be assessed using the endocrine subscale of the Functional Assessment of Cancer Therapy-Endocrine Symptom questionnaire. The Endocrine Subscale was designed for use with the FACT-B (Functional Assessment of Cancer Therapy for breast cancer patients) but has been tested on its own¹⁰⁵. It comprises 18 items in which patients indicate how true a statement has been for them over the prior 7 days using a 5-point scale.

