- Disturbance in sleep or sleep changes on therapy will be evaluated with the NIH PROMIS Adult Sleep Disturbance Version 1.0 Short Form. The sleep disturbance item bank assesses self-reported perceptions of sleep quality, sleep depth, and restoration associated with sleep over the 7 days before questionnaire administration. This includes perceived difficulties and concerns with getting to sleep or staying asleep, as well as perceptions of the adequacy of and satisfaction with sleep¹⁰⁶.
- Changes in sexual function will be evaluated using the MOS Sexual Functioning Scale, which consists of four items assessing interest in sex, ability to relax and enjoy sex, arousal, and ability to have an orgasm. Items are rated on a 5-point scale (1=not a problem, 2=little of a problem, 3=somewhat of a problem, 4=very much of a problem, and 5=not applicable). This scale is useful for measuring sexual function in both men and women. It has demonstrated good reliability and construct validity in breast cancer patients 107.
- Medication adherence will be assessed using the institutional drug diary (APPENDIX G).

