APPENDIX E: PRO Questionnaire

The following represents the questions to be asked in the REDCap survey.

CLINICAL AND DEMOGRAPHIC INFROMATION

T	T.	
I.	Demograp)hics:
		,,,,,,,,,,,,,,,,,,,,,,,,,,,,,,,,,,,,,,,

- a. What is your date of birth?
- b. What is your age?
- c. Are you Hispanic or Latino?
 - i. Yes
 - ii. No
- d. What is your race?
 - i. White/Caucasian
 - ii. Black or African American
 - iii. Asian
 - iv. Native Hawaiian or Pacific Islander
 - v. American Indian or Alaska Native
 - vi. Other, _____

II. Past Medical/social/family history

- 1. Have you had a menstrual period in the past 12 months?
 - a. Yes
 - b. No
- 2. If you have not had a menstrual period in the last 12 months, at what age did you stop having periods? (free text)
- 3. During the past year how many alcoholic beverages did you have?
 - a. Never or less than 1 per month
 - b. 1-3 per month
 - c. 1 per week
 - d. 2-4 per week
 - e. 5-6 per week
 - f. 1 per day
 - g. 2-3 per day
 - h. 4-5 per day

- i. More than 5 per day
- 4. Have you ever smoked?
 - a. Yes
 - b. No
- 5. If you have ever smoked, please indicate how many cigarettes you smoked when you were smoking:
 - a. Never smoked
 - b. Less than one-half pack per day
 - c. One-half to one pack per day
 - d. Two packs per day
 - e. Three packs per day
 - f. More than three packs per day
- 6. If you have ever smoked, please indicate how many years you smoked:
 - a. One year
 - b. 2-5 years
 - c. 6-10 years
 - d. 11-15 years
 - e. 16-20 years
 - f. 21-25 years
 - g. 26-30 years
 - h. 31-35 years
 - i. >35 years

III. Medications

- 1. Which of the following medications are you taking? (Select all that apply)
 - a. Tamoxifen
 - b. Raloxifene (Evista)
 - c. Anastrozole (Arimidex)
 - a. Letrozole (Femara)
 - b. Exemestane (Aromasin)
 - c. Goserelin (Zoladex)
 - d. Leuprolide (Lupron)

IV. Patient Reported Outcomes (PROs) - Sleep

In the	past month				
1.	During the past month, what time have you usually gone to bed at night?				
	I	BED TIME	-		
2.	2. During the past month, how long (in minutes) has it usually taken you to fall asleep each nig				
	1	NUMBER OF MINUTES	S		
3. During the past month, what time have you usually gotten up in the morning?				morning?	
	(GETTING UP TIME			
4.	During the past month, how many hours of actual sleep did you get at night? (This may be different than the number of hours you spent in bed.)				
	I	HOURS OF SLEEP PER	NIGHT		

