APPENDIX F: Score Interpretation

NOTE: Please see below an example of the information to be provided to the participant upon completion of the questionnaires. This information will be also available to the providers to discuss with participants during their clinic visit.

The reports produced by the system will highlight scores that are potential 'problems' because they represent either particularly poor health, quality of life below average, or significant worsening from the last time point, as follows:

Sleep Disturbance, Physical Function, Anxiety, Depression, Pain Impact, and Fatigue:

- Higher scores represent more of what is being measured (e.g., higher scores indicate better physical function and worse fatigue).
- A score of 30-70 is considered within the expected range of an average population of patients.
- Highlighted scores are either outside of that range (less than 30 for physical function; greater than 70 for all others) or are a significant change from previous answers.

Sexual Function:

- Higher scores indicate more problems with sexual function.
- A score of less than 40 is considered to be within the expected range of an average population of patients.
- Highlighted scores are above that average range (greater than 40) or a significant increase from previous answers.

Endocrine Symptoms:

- Higher scores indicate better quality of life.
- A score of 41.3 76 is considered to be within the expected range for an average population of women.
- Highlighted scores are below that average range (less than 41.3) or a significant decrease from previous answers.

Godin Leisure-Time Exercise questionnaire

- For the first question, weekly frequencies of strenuous, moderate, and light activities are multiplied by nine, five, and three, respectively.
- Total weekly leisure activity is calculated in arbitrary units by summing the products of the separate components, as shown in the following formula: Weekly leisure activity score = $(9 \times \text{Strenuous}) + (5 \times \text{Moderate}) + (3 \times \text{Light})$.
- For example: Strenuous = 3 times/wk. Moderate = 6 times/wk, and Light = 14 times/wk. Then, the total leisure activity score = $(9 \times 3) + (5 \times 6) + (3 \times 14) = 27 + 30 + 42 = 99$.
- Godin scale score of ≥24 is active, 14-23 is moderately active, and <14 is insufficient active or sedentary.

Statistical Considerations

Sleep Disturbance, Physical Function, Anxiety, Depression, Pain Impact, and Fatigue:

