- Surveys were validated in the general population.
- All of these domains are mapped to a mean score of 50, with a standard deviation of 10.
- Highlighted scores represent a score more than 2 standard deviations from the mean (20 points) or a worsening of at least half a standard deviation (5 points).

Sexual Function:

- This survey was validated in patients with major medical problems with and without depression, and patients without medical problems but with depression.
- For this population, the mean sexual problem scores ranged from 24.48 43.5, with a standard deviation of 32.
- Highlighted scores represent a score that is worse than the average scores among an ill population (40 points) or a worsening of at least half a standard deviation (16 points).

Endocrine Symptoms:

- This survey was validated in female breast cancer patients undergoing a variety of hormone therapies as well as normal controls.
- This survey is mapped to a mean score of 59.7, which is the total group mean from the validated population, with a standard deviation of 9.2.
- Highlighted scores represent a score that is two standard deviations away from the mean (41.3 points) or a worsening of at least half a standard deviation (4.6 points).

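### The sleep PRO is named and scored as a 7-day PROMIS T-score, but Appendix E asks past-month items to which that scoring cannot be applied

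*Combined protocol and SAP*

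**What the plan says.** Three parts of the combined protocol and SAP bear on the sleep measure.

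- **Section 7.5.2 (instrument).** The overview states: "Pain, fatigue, mental well-being, sleep, and physical function will be assessed using the NIH PROMIS questionnaire". The sleep bullet is specific: "Disturbance in sleep or sleep changes on therapy will be evaluated with the NIH PROMIS Adult Sleep Disturbance Version 1.0 Short Form". It describes perceptions of sleep quality, depth and "restoration associated with sleep over the 7 days before questionnaire administration".
- **Section 7.5.2 (scoring).** The fatigue bullet gives a rule for the whole PROMIS family: "As with all of the PROMIS short forms, each question has five response options ranging in value from one to five". The responses are summed to a raw score, which a conversion table turns into a T-score.
- **Appendix E, section IV (items asked).** The appendix is introduced as the content of the REDCap survey. Its only sleep section begins "During the past month, what time have you usually gone to bed at night" and keeps the past-month frame throughout.
- **Appendix F (score interpretation).** Sleep falls under the group headed "Sleep Disturbance, Physical Function, Anxiety, Depression, Pain Impact, and Fatigue", of which it says: "All of these domains are mapped to a mean score of 50, with a standard deviation of 10". The expected range is 30-70. A score is highlighted if it lies more than 20 points from the mean or has worsened by at least 5 points.

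**The concern.** The instrument named, the items asked and the scoring rule should describe one questionnaire. For sleep, 7.5.2 and Appendix F describe one and Appendix E prints another. If REDCap is built from Appendix E, the data will not fit the only scoring rule the plan gives.

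Two uses are affected. First, PROs form part of secondary objectives 4.2.1 and 4.2.2 and exploratory objective 4.3.2, and section 13.1 lists them among the secondary endpoints at baseline, 2 and 6 months. Sleep would enter those analyses with no defined score. If a score were chosen after the answers had been seen, the choice would be post hoc. Second, Appendix F describes reports for participants, also available to providers for clinic discussion. Their sleep range and worsening flag would have nothing valid to work on.

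**Working it through.** No design figure depends on this, so the check is a comparison of the sections.

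| Feature | 7.5.2 and Appendix F | Appendix E, section IV |
|---|---|---|
| Instrument | PROMIS Adult Sleep Disturbance v1.0 Short Form | Not named |
| Recall | 7 days | Past month |
| Items 1-4 | Five options valued 1 to 5 | Open entries: bed time, minutes to fall asleep, getting-up time, hours slept |
| Remaining items | Five options valued 1 to 5 | Four response categories |
| Score | Raw sum, then T-score by table | No rule given |

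**Step 1: the Appendix F rule is coherent for a T-score.** With mean 50 and SD 10, two SDs either side give 50 − 2 × 10 = 30 and 50 + 2 × 10 = 70, and half an SD is 10 / 2 = 5. These reproduce the stated range and flag.

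**Step 2: the rule needs an input that Appendix E does not supply.** The conversion table takes a sum of item values, each from 1 to 5. A clock time, a number of minutes or a number of hours is not such a value. A four-category frequency item is not a five-option PROMIS item either, and the documents give no mapping from one to the other. The recall period differs too, so answers about a month cannot later be turned into answers about 7 days.

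**Step 3: this is not a fault of text extraction.** The past-month stems and four-category responses are legible through the whole sleep section. In the same appendix the anxiety, depression, pain and fatigue sections show a 7-day recall and five options, as 7.5.2 describes. No 7-day, five-option sleep items appear elsewhere in the appendix.

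**Step 4: extent.** Section 13.1 plans 55 women, and PROs are collected at three time points: 55 × 3 = 165 sleep questionnaires at most. Individual objectives use fewer. Objective 4.2.1 concerns SLOW-BWL women who reach 5% loss; at the design alternative of 29% that is 0.29 × 30 = 8.7, or about 9 women. Objective 4.2.2 is a baseline comparison within SLOW-BWL.

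**The case against.** Several points on the other side have force.

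- **The answers keep their value.** A reader might infer that the sleep domain is lost for all 55 women. The documents do not support that. Bed time, minutes to fall asleep, hours slept, frequency of trouble sleeping and overall quality can be interpreted and compared over time with the methods of 13.2. Section 7.3 also lists sleep among the Fitbit process variables. What cannot be obtained is the PROMIS T-score. This stands.
- **Appendix F governs reports, not analysis.** It presents itself as an example of feedback, and 13.2 uses none of its cut-offs. This stands for the flags. It does not close the gap, because 7.5.2 itself sets T-score scoring for all PROMIS short forms and no other sleep rule exists.
- **Misleading flags are not certain.** With no valid input, the result may be no sleep flag at all. The documents support only that the input is undefined.
- **The appendix may be out of date.** Its nutrition section still refers to a different online platform, so the live REDCap form may differ. But 7.5.2 and the opening of Appendix E both say that the appendix holds the REDCap questions.
- **Perhaps the items are the Pittsburgh Sleep Quality Index.** Section 5.10 mentions that index, but only as used in the POWER study. Nothing identifies it as an instrument of this trial, and Appendix F has no scoring for it.

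**Conclusion.** This is an internal inconsistency, and the plan is wrong as written on this point. The sleep scoring in 7.5.2 and Appendix F cannot be applied to the items in Appendix E, section IV. As it stands, the sleep PRO has no valid scoring rule, and the sleep range and worsening flag in the participant and provider reports have no defined input.

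The consequence is confined to one PRO domain within secondary objectives 4.2.1 and 4.2.2, exploratory objective 4.3.2 and the Appendix F reports. The primary endpoint, the two-stage design and the primary PRO (physical function, section 5.10) do not depend on it.

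The conclusion assumes that the REDCap form follows Appendix E, as the documents state. It does not depend on which published instrument the past-month items come from.

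**What to change.** Reconcile 7.5.2, Appendix E and Appendix F. The route depends on whether baseline questionnaires have been collected, which the documents do not establish.

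1. **None collected, and PROMIS is intended.** Replace the sleep items in Appendix E with the PROMIS short form named in 7.5.2. Appendix F can then stand.
2. **Some collected, or the past-month instrument is intended.** Keep the past-month items at baseline, 2 and 6 months. Name the instrument in 7.5.2, and replace the T-score rule and flags for sleep in Appendix F with that instrument's own scoring, fixed before the data are analysed. Swapping forms part-way would break the comparison of follow-up with baseline.

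The cost is a small amendment and a change to the REDCap form or report. Under route 2 there is no PROMIS T-score for sleep. The effect of route 1 on participant burden cannot be judged, because 7.5.2 gives no item count for the PROMIS sleep form. Neither route changes sample size, visits or treatment.

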÷	If you	mark "Ner	ver" for a	question	, follow ti	ne "Go to	instruct	ion.		
٠	Choos	e the best	answer	for each o	question.	Mark onl	y one res	ponse fo	or each qu	estion.
1.5	orange,	e last mont apple, gra ry juice drir	pe, or gra	pefruit juic	e? Do no	ot count fr	uit drinks	like Kool-	Aid, lemor	e such as nade, Hi-C, petween meals.
	0	0	0	0	0	0	0	0	0	0
	Never (Go to	1-3 times	1-2 tmes	3-4 times	5-6 times	1 time	2 times	3 times	4 times	5 or more times
0	aution 2)	last month	-	per wook	per week	per day	per day	per day	per day	per day
1a.	Less th	ne you drai O an % cup i 6 ounces)		% to 1% (6 to 10 ou	cup		lly drink? Vi to 2 cup to 16 ouns			than 2 cups nan 16 ounces)
2.		esh, canne								t any kind of times and for
	0	0	0	0	0	0	0	0	0	0
	(Go to	1-3 times	1-2 tmes	3-4 times	5-6 times	time	times	3 times	times	5 or more times
	(C moltes)	tast month	per wook	per wook	per week	per day	per day	per day	perday	per day
0										
	Each tin	ne you ate	fruit, how	much did	you usua	illy eat?				
	Each tin	ne you ate	fruit, how	much did	you usua	illy eat?	0			0
2a.		ne you ate		r much did O 1 medium	fruit	100	O medium fru	iits	More than	On 2 medium fruits

	lavar	1-3	1-2	34	5-6	0	0	0	0	5 or more
	3o to	timos	timas	timas	times	tima	timas	times	timas	times
Line	ston 4)	tast month	perwook	per wook	per waak	per day	perday	per day	per day	per day
В.	Each tir	ne you ate	lettuce s	alad, how	much did	you usual	ly eat?			
	. About	0		0			0			0
	ADOL	£ 16 cup		About 1	oup	139	About 2 cup	4	More	than 2 cups
w	Over the	e last mont	h, how of	en did you	u eat Fren	ch fries o	r fried po	tatoes?		
	0	0	0	-0	0	0	0	0	0	0
	lavar	1-3	1-2	3-4	5-6	.1	. 2	3	. 4	5 or more
	So to eston 5)	timos last month	times per week	per week	per wook	per day	per day	per day	per day	per day
a.	Each tir	ne you ate	French fo	ries or frie	ed potatoe	s, how m	uch did yo	ou usually	eat?	
	10" 10"	0		0	127		0		2 72	0
	Small order or less Medium order (About 1 cup or less) (About 1% cups)				Large order	Super Size order or more (About 3 cups or more)				
	(About 1	cup or less)		(About 1%	cups)		About 2 cup	5)	(About	a cups or more)
		e last mont es, potato						Count ba	ked, boile	ed, and mashe
	0	0	0	0	0	0	0	0	0	0
	Bo to	1-3 times	1-2 times	3-4 timos	5-6 times	timo	times	times	times.	5 or more times
	ston 6)			per wook		per day	perday	per day	per day	per day
3.	Each tir	ne you ate	these po	tatoes, ho	w much d	id you usu	ally eat?			
	3	03		0			0			0
		otato or less		1 medium p			large potat			potatoes or mon
	(se con	or less)		(% to 1 a	mb)		1 to 1% cup	5)	(136.0	sups or more)
		e last mont beans, po					beans? (Count bak	ed beans	, bean soup,
9	0	0	0	0	0	0	0	0	0	0
	lover 30 to	1-3 timos	times	3-4 times	5-6 times	timo	2 times	3 times	times	5 or more times
	ston 7)	Control of the Contro	per wook		per wuok	perday	per day	per day	per day	per day
в.	Each tir	ne you ate	these be	ans, how	much did y	you usuall	y eat?			
	. manual s	0		0	leger.		0 1 to 1% cup		122000	0
		an 16 cup		16 to 1 o	UID .		1 10 1% cup		More	than 1% cups

	DO	NOT COU	. v	exican dis	pes				elets, cas	seroles,
		cou	NT: · A	other ve	getables-	raw, cool	ked, canne	ed, and fro	zen	
0	O Never (Go to usestion 6)	1-3 times	1-2 tmos	3-4 times k per wee	5-6 times k per week	1 time per day	times per day	3 times per day	times per day	5 or more times per day
7a.	Each	of these tir	nes that y	ou ate oth	er vegeta	bles, how	much did	you usua	lly eat?	
	Less	than 1/5 cup		% to 1	cup		1 to 2 cup	os.	Mor	O no than 2 cups
8.		the last mo				nato sauc	e? Include	e tomato s	sauce on p	oasta or
a	O Never (Go to uestion 9)	1-3 times	1-2 times	3-4 times per wee	5-6 times	1 time per day	2 times per day	3 times per day	times per day	5 or more times per day
8a.	Each	time you a	te tomato	sauce, h	ow much d	id vou us	ually eat?			
	70.) Wang		About % o		125	O Noout 1 cup		More	O than 1 cup
9.	Over with v	the last mo	onth, how o	often did y strone sou	ou eat veg	etable so er soups	oups? Inc	lude toma vegetable	ito soup, g	jazpacho, be
	0	0	0	0	0	0	0	0	0	0
	Novor	1-3	1.2	3-4	5-6	1	2	3	4	5 or more
Ou	(Go to partico 10	timos last mon	times th per wea	times per wee	times k per wool	per day	per day	per day	perday	times per day
9a.	Each	time you a	te vegetal	ole soup,	how much	did you u	sually eat	?		
	Less th	an 1 cup		1 to 2 cu	ps	eneroni E	O 2 to 3 cups		More t	Constant 3 cups
10.	Over sandy	the last mo viches, cas	onth, how o	often did y tews, stir-	ou eat mix fry, omelet	tures that s, and tac	t include	d vegetab	oles? Cou	nt such food:
	0	0	0	0	0	0	0	0	0	0
	Navor	1-3 timos	1-2 times	3-4 times	5-6 tmos	time	2 times	times	4 times	5 or mora times
		last month		per wook		per day	per day	per day	per day	per day
			Dinig	Expent* by WEB	Previous or U.S.	A. Wart Refe	HOTW ZEIGHT	Sept. 14000	1	and the second
		P			much for ne enclose					

ID # Place Label Here

NATIONAL CANCER INSTITUTE QUICK FOOD SCAN

 Think about your eating habits over the past 12 months. About how often did you eat or drink each of the following foods? Remember breakfast, lunch, dinner, snacks, and eating out. Blacken in only one bubble for each food.

TYPE OF FOOD	Never	Less than Once Per Month	1-3 Times Per Month	1-2 Times Per Week	3-4 Times Per Week	S-6 Times Per Week	Time Per Day	2 or More Times Per Day
Cold cereal	0	0	0	0	0	0	0	0
Skim milk, on cereal or to drink	0	0	0	0	0	0	0	0
Eggs, fried or scrambled in margarine, butter, or oil	0	0	0	0	0	0	0	0
Sausage or bacon, regular-fat	0	0	0	0	0	0	0	0
Margarine or butter on bread, rolls, pancaties	0	0	0	0	0	0	0	0
Orange juice or grapefruit juice	0	0	0	0	0	0	0	0
Fruit (not juices)	0	0	0	0	0	0	0	0
Beef or park hot dogs, regular-fat	0	0	0	0	0	0	0	0
Cheese or cheese spread, regular-fat	0	0	0	0	0	0	0	0
French fries, home fries, or hash brown potatoes	0	0	0	0	0	0	0	0
Margarine or butter on vegetables, including potatoes	0	0	0	0	0	0	0	0
Mayonnaise, regular-tat	0	0	0	0	0	0	0	0
Salad dressings, regular-fat	0	0	0	0	0	0	0	0
Rice	0	0	0	0	0	0	0	0
Margarine, butter, or oil on rice or pasta	0	0	0	0	0	0	0	0

			-		
		0	0		O
DIDN T USE	Almost	About 1/4	About 1/2	About 3/4	Almost always
MARGARINE	never	of the time	of the time	of the time	or always
Overall, when y medium, or low i		foods you ate over t	he past 12 month	ns, would you say	your diet was high
나는 아이들에 빠르게 되었다면 때		foods you ate over t	he past 12 monti	os, would you say	your diet was high

